4.1.2. Baseline Definition

For all endpoints unless otherwise specified the baseline value will be the latest pre-dose assessment with a non-missing value, including those from unscheduled visits. If time is not collected, Day 1 assessments are assumed to be taken prior to first dose and used as baseline. For participants who did not receive study treatment during the study, baseline will be defined as the latest, non-missing collected value.

Unless otherwise stated, if baseline data is missing no derivation will be performed and baseline will be set to missing.

4.1.3. Multicenter Studies

In this multicenter global study, enrollment will be presented by country and site.

Data from all participating centers will be integrated and no controlling for center-effect will be considered in the statistical analyses. It is anticipated that participant accrual will be spread thinly across centers and summaries of data by center would unlikely be informative and will not be provided.

4.2. Primary Endpoint(s) Analysis

4.2.1. Definition of Endpoint(s)

Overall Survival (OS)

Overall Survival (OS) is defined as the interval of time from the date of randomization to the date of death due to any cause.

Participants without documented death will be censored at last known alive date. The last date will be determined by the maximum collection/assessment date from among selected data domains within the clinical database; details will be provided in a separate Output and Programming Specification (OPS) document.

Progression-Free-Survival (PFS) per RECIST v1.1

Progression-free-survival (PFS) per RECIST v1.1 by investigator assessment is defined as the time from the date of randomization to the date of the first objectively documented disease progression per RECIST v1.1 based on investigator assessment, or death due to any cause, whichever occurs first.

The date of disease progression is defined as the date of radiological disease progression based on imaging data per RECIST v1.1. For cases where symptomatic progression is documented by the investigator, the derived response based on tumor assessment data will be utilized.

For participants who receive subsequent anticancer therapy, the following rules will apply:

- If a participant has only a baseline visit or does not have an adequate post-baseline radiological assessment on or prior to the date of initiation of anticancer therapy, PFS will be censored at the date of randomization.
- If anticancer therapy is started without documented disease progression or is started prior to documented disease progression, then PFS will be censored at the date of the last adequate radiological assessment on or prior to the initiation of anticancer therapy (i.e., if an assessment occurs on the same day as the start of new anticancer therapy, the assessment will be used as it is assumed that the assessment occurred prior to the administration of new anticancer therapy). The date of the last adequate radiological assessment will be used as the censoring date.

- If the start date of anticancer therapy is partial, the imputation rules described in the OPS will be applied.

Since PFS is interval censored, extended loss to follow-up prior to PD or death increases the uncertainty when the event occurs. As such, PFS will be analyzed censoring for extended time without an adequate assessment to account for missed response assessments prior to disease progression or death. Specifically, if there are two or more assessments which are missing followed by an assessment of PD or death, PFS will be censored at the last adequate assessment prior to PD or death.

A summary of the assignments for progression and censoring dates for the primary analysis of PFS per RECIST v1.1 is also illustrated in [Table 3](#).

Table 3 Censoring Rules for Primary Analysis of PFS per RECIST v1.1

Situation	Primary Analysis
No or incomplete baseline disease assessments and the participant has not died	Censored at the date of randomization
No adequate ¹ post-baseline disease assessments (prior to anticancer therapy, if initiated) and the participant has not died ²	Censored at the date of randomization
With adequate post-baseline disease assessments, new anticancer treatment is not initiated, and no documented PD or death	Censored at the date of last adequate radiological disease assessment
With adequate post-baseline disease assessments before the start of new anticancer therapy, and new anticancer treatment is initiated (prior to documented PD or death) ³	Censored at the date of last adequate radiological disease assessment on or prior to starting new anticancer treatment
PD or death documented after ≤ 1 missed disease assessment ⁴	Progressed at the date of documented PD ⁵ or death, whichever occurs first
PD or death documented after ≥ 2 missed disease assessments ^{4,6}	Censored at the date of last adequate radiological disease assessment prior to the ≥ 2 missed disease assessment ⁷

Abbreviations: CR=complete response; PD=progressive disease; PFS=progression-free survival; PR=partial response; RECIST=response evaluation criteria in solid tumors; SD=stable disease

1. An adequate assessment is defined as an assessment where the investigator assessed response is CR, PR, or SD
2. In case participant has documented PD but no other adequate assessments, see scenarios below.
3. If PD and new anti-cancer therapy occur on the same day, it is assumed that the progression was documented first (i.e., outcome is progression; the date is the date of the assessment for progression).
4. The case where PD or death documented after the initiation of new anticancer treatment is described above and is not included in this situation.
5. The earliest of (i) Date of radiological assessment showing new lesion (if progression is based on new lesion); or (ii) Date of radiological assessment showing unequivocal

- progression in non-target lesions, or (iii) Date of last radiological assessment of measured lesions (if progression is based on increase in sum of measured lesions).
6. Refer to Section 5.3 for details in extended time without an adequate assessment.
 7. The date of randomization will be used if there are no adequate post-baseline assessments.

4.2.2. Main Analytical Approach

Due to early study termination, only the main analytical approaches using primary estimands will be completed for the main CSR.

Overall Survival (OS)

The non-parametric Kaplan-Meier method will be used to estimate the survival curves for OS. Kaplan-Meier plots of OS will be presented by study intervention. Kaplan-Meier estimates for the median overall survival and the first and third quartiles will be presented, along with 95% CIs. CIs for quartiles will be estimated using Brookmeyer-Crowley method (1982). The treatment difference in survival will be assessed by the stratified log-rank test.

A stratified Cox proportional hazard model with Efron's method of tie handling will be used to assess the magnitude of the treatment difference (i.e., the hazard ratio). The hazard ratio (HR) and its corresponding 95% confidence interval from the stratified Cox model with a single treatment covariate will be reported separately for the total and PD-L1 CPS ≥ 1 populations.

If PFS is significant in both the total and PD-L1 CPS ≥ 1 populations for superiority of GSK3359609 in combination with pembrolizumab + 5FU/platinum-based chemotherapy compared to placebo in combination with pembrolizumab + 5FU/platinum-based chemotherapy, OS in the total population will be tested at the 2.5% alpha level. Otherwise, OS in the total population will be tested at the 2.49% alpha level. OS in the PD-L1 CPS ≥ 1 population is tested sequentially at the same overall alpha level as that of OS in the total population. If OS is not significant in total population, the formal conclusion of statistical significance on OS in PD-L1 CPS ≥ 1 population will not be drawn.

Statistical Methodology Specification

Endpoint / Variables

 • OS
Model Specification

 • OS will be estimated using Kaplan-Meier analysis for each study intervention (PROC LIFETEST). The median, 25th and 75th percentiles of OS will be estimated and corresponding 95% Confidence intervals will be estimated using the Brookmeyer-Crowley method (1982). • Comparison of distributions of OS between study interventions will be based on the stratified log-rank test (PROC LIFETEST).

- A stratified Cox proportional hazard model with Efron's method of tie handling and study intervention as the sole explanatory variable will be used to assess the magnitude of the treatment difference (i.e., the hazard ratio) in OS between study interventions (PROC PHREG).

Model Checking & Diagnostics

 • The proportional hazards assumption will be assessed prior to model fitting using the following methods: 
 ○ Kaplan-Meier plot by study intervention: A non-parallel pattern is an indication of violation of the proportional hazard assumption. ○ Plot of $\log(-\log(\text{survival}))$ versus $\log(\text{time})$ by study intervention: A non-parallel pattern is an indication of violation of the proportional hazard assumption. ○ Plot of Schoenfeld residuals versus time: A non-zero slope is an indication of a violation of the proportional hazard assumption. ○ Evaluation of time-dependency of treatment effect by adding an interaction term of treatment and time in the Cox model. If the interaction term is significant ($p < 0.05$), it is considered that the proportional hazards assumption is violated. • If one or more of the procedures above demonstrates clear violation of the proportional hazards assumption in OS, it is considered the proportional hazards assumption does not hold. Hazard ratio and corresponding 95% CI estimated from the Cox model will still be reported.
Model Results Presentation

 • Kaplan-Meier estimates for the median overall survival and the first and third quartiles will be presented, along with 95% CIs. • The p-value from the stratified log-rank test will be reported. • The hazard ratio and the corresponding 95% confidence interval from the Cox model will be reported.
Subgroup Analyses

 • The stratified log-rank test and Cox proportional hazard model proportional hazard model analysis will be repeated in the subgroup analyses defined in Section 4.2.5 if data permit.

Progression-Free Survival per RECIST v1.1 (PFS)

A stratified Cox proportional hazard model with Efron's method of tie handling will be used to assess the magnitude of the treatment difference (i.e., the hazard ratio). The hazard ratio and its 95% confidence interval from the stratified Cox model with a single treatment covariate will be reported for the total and the PD-L1 CPS ≥ 1 participants.

Kaplan-Meier plots of PFS will be presented by study intervention. Summaries of number and percentage of participants experiencing a PFS event and the type of event (PFS per RECIST v1.1 or death) will be provided along with median PFS and the first and third quartiles and 95% CIs for each treatment.

Statistical Methodology Specification

Endpoint / Variables

 PFS per RECIST v1.1 based on investigator assessment
Model Specification

 PFS will be analyzed across study interventions using Kaplan-Meier analysis (PROC LIFETEST). The median, 25th and 75th percentiles of PFS will be estimated and corresponding 95% Confidence intervals will be estimated using the Brookmeyer-Crowley method (1982). Comparison of distributions of PFS between study interventions will be based on the stratified log-rank test (PROC LIFETEST). A stratified Cox proportional hazard model with Efron's method of tie handling and study intervention as the sole explanatory variable will be used to assess the magnitude of the treatment difference (i.e., the hazard ratio) in PFS between the study interventions (PROC PHREG).
Model Checking & Diagnostics

 The proportional hazards assumption will be assessed prior to model fitting using the following methods: 
 Kaplan-Meier plot by study intervention: A non-parallel pattern is an indication of violation of the proportional hazard assumption. Plot of log(time) against log(-log(survival)) by study intervention: A non-parallel pattern is an indication of violation of the proportional hazard assumption. Plot of Schoenfeld residuals for treatment: A non-zero slope is an indication of a violation of the proportional hazard assumption. Evaluation of time-dependency of treatment effect by adding an interaction term of treatment and time in the Cox model. If the interaction term is significant ($p < 0.05$), it is considered that the proportional hazards assumption is violated. If one or more of the procedures above demonstrates clear violation of the proportional hazards assumption in PFS, it is considered the proportional hazards assumption does not hold. Hazard ratio and corresponding 95% CI estimated from the Cox model will still be reported.
Model Results Presentation

 Kaplan-Meier estimates for the median PFS and the first and third quartiles will be presented, along with 95% CIs. The p-value from the stratified log-rank test will be reported. Hazard ratio and corresponding 95% confidence interval from the Cox model will be reported.

4.2.3. Sensitivity Analyses

Due to early study termination, sensitivity analyses will not be performed for the main CSR.

4.2.4. Supplementary Analyses

Due to early study termination, supplementary analyses will not be performed for the main CSR.

4.2.5. Subgroup analyses

Due to early study termination and minimal available data, subgroup analyses will not be performed for the main CSR.

4.3. Secondary Endpoint(s) Analysis

4.3.1. Key/Confirmatory Secondary Endpoint(s)

4.3.1.1. Definition of Endpoint

Time to Deterioration (TTD) in Pain and Physical Function (PF)

Time to deterioration (TTD) is defined as the time from randomization to the first definitive meaningful deterioration from baseline in the EORTC IL51 pain domain score and the TTD in Physical Function (PF) score. Deterioration is defined as an increase in the EORTC IL51 pain domain and a decrease in physical function as measured by the PROMIS-PF-8c. Specifically, the deterioration has to be:

- Meaningful, i.e. greater than a clinically meaningful within-individual change in score, as defined below;
- Definitive, i.e. all subsequent assessment of the score are also showing a clinically meaningful deterioration compared with baseline, or no further score is available for the participants for any reason (including discontinuation, disease progression or death).

Participants who don't show meaningful deterioration will be censored at the time of the last available PRO assessment within the pain domain of EORTC IL51 for TTD in pain or within PROMIS-PF-8c for TTD in PF. For TTD in pain or TTD in PF, the determination of dates of deterioration events and dates for censoring are summarized in [Table 4](#).

Table 4 Censoring Rules for Analysis of TTD

Situation	Primary Analysis
No or incomplete baseline corresponding PRO assessments	Censored at the date of randomization
No post-baseline corresponding PRO assessments	Censored at the date of randomization
With post-baseline corresponding PRO assessments, new anticancer treatment is not initiated, and no deterioration	Censored at the date of last available corresponding PRO assessment
With post-baseline corresponding PRO assessments, and new anticancer treatment is initiated (prior to deterioration) ¹	Censored at the date of last available corresponding PRO assessment on or prior to starting new anticancer treatment
Deterioration after ≤ 1 missed corresponding PRO assessment ²	Deteriorated at the date of deterioration
Deterioration after ≥ 2 missed corresponding PRO assessments if at least one missed assessment is due to the participant being too ill ^{2,3}	Censored at the date of last available corresponding PRO assessment prior to the ≥ 2 missed corresponding PRO assessment

1. If deterioration and new anti-cancer therapy occur on the same day, it is assumed that the deterioration was documented first (i.e. outcome is deterioration; the date is the date of deterioration).
2. The case where deterioration observed after the initiation of new anticancer treatment is described above and is not included in this situation.
3. In the case of deterioration after ≥ 2 missed corresponding PRO assessments and all missed assessments are due to reason other than that participant is too ill, it censors at the date of last corresponding PRO assessment on or prior to starting new anticancer treatment as the situation of with post-baseline corresponding PRO assessments, and new anticancer treatment is initiated (prior to deterioration), i.e. missing corresponding PRO assessments are ignored in this case. Refer to Section 5.3 for details in extended time without an adequate assessment.

As no threshold for meaningful within-individual change is established for the EORTC IL51 pain domain score or PROMIS-PF-8c score, the value for use in the TTD analyses will be determined using pooled blinded data from study 209229 and 209227. The threshold may be finalised following study database lock and will be reported in the main CSR. The full procedure for determination of meaningful within- individual change in EORTC IL51 pain domain score and PROMIS-PF-8c score will be fully described in a standalone SAP. It will include using an anchor-based approach that utilizes the patient global impression of severity and change as an anchor, and possibly other clinical anchors (e.g. ECOG status). Supportive distribution-based methods may be applied as the sensitivity analysis.

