The overall proportion of participants by PD-L1 CPS status will be capped such that the maximum proportion of participants in PD-L1 CPS ≥ 20 , $1 \leq \text{CPS} < 20$ or CPS < 1 will not exceed the expected proportion by 5% for any subgroup. Refer to Section 9.2 for the expected sample size of each subgroup.

Intervention Groups and Duration:

The study is comprised of three periods: screening, treatment, and follow-up. The total duration of study participation begins with the signing of the informed consent form (ICF). After a screening period of up to 45 days, eligible participants will be randomly assigned to 1 of the 2 treatment arms.

For participants who meet all eligibility criteria and are randomized within the study, the maximum duration of treatment with pembrolizumab, GSK3359609 and placebo is

expected to be approximately 2 years, up to 35 cycles. The duration of chemotherapy treatment will be 6 cycles (cycle=21 days). If the course of chemotherapy treatment is completed after six cycles or discontinued prior to completion of 6 cycles, GSK3359609, placebo and pembrolizumab treatment may continue for the aforementioned duration indicated.

The follow-up period begins when study treatment is permanently discontinued; participants will undergo follow-up assessments for safety, patient reported outcomes, PFS on first subsequent anti-cancer therapy (PFS2), subsequent anticancer therapy and survival as indicated in the Schedule of Activities (SoA); refer to Section 1.3. The total duration of study participation begins with the signing of the ICF through the final protocol-defined follow-up assessment for survival.

Participants will be randomly assigned to one of the following combinations:

- GSK3359609 24 mg + pembrolizumab 200 mg + 5FU 1000 mg/m²/24 hours for 4 days + platinum chemotherapy (cisplatin 100 mg/m² OR carboplatin area under the curve [AUC] 5) Q3W for 6 cycles (Arm 1)
- Placebo + pembrolizumab 200 mg+ 5FU 1000 mg/m²/24 hours for 4 days + platinum chemotherapy (cisplatin 100 mg/m² OR carboplatin AUC 5) Q3W for 6 cycles (Arm 2)

GSK3359609 and pembrolizumab are administered as 30-minute intravenous (IV) infusions. GSK3359609 will be administered first followed by pembrolizumab; 5FU-platinum chemotherapy will be administered after pembrolizumab infusion is complete. The sequence in which chemotherapy doublets are administered is per standard practice.

[figure not shown]
Independent Data Monitoring or Other Committee:

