9.4.3. Patient Reported Outcomes

EORTC IL50 and IL51(subset of domains from the EORTC QLQ C30 and H&N35 respectively) are not pure efficacy or safety endpoints because they are affected by both disease symptoms and treatment tolerability in addition to HRQoL domains.

The time to deterioration (TTD) in Pain measured by the EORTC QLQ-H&N35 pain domain (included in the EORTC IL51) and the TTD in Physical Function (PF) measured by the PROMIS PF 8c will be analysed in the ITT population using the non-parametric Kaplan-Meier method.

The treatment effect in TTD will be assessed separately by the stratified log-rank test. A stratified Cox proportional hazard model with Efron's method of tie handling will be used to assess the magnitude of the treatment difference (i.e., hazard ratio) between the treatment arms. The hazard ratio and its 95% confidence interval from the stratified Cox model with Efron's method of tie handling and with a single treatment covariate will be reported.

For both Pain and PF, TTD will be defined as the time from the date of randomization to the date of first definitive meaningful deterioration in score compared to baseline. The deterioration has to be:

- Meaningful, i.e. greater than a clinically meaningful within-individual change in score, as defined below;
- Definitive, i.e. two sequential assessments of the score are showing a clinically meaningful deterioration compared to baseline and no subsequent scores return to baseline, or no further score is available for the patients for any reason (including disease progression or death)

Patients who don't show meaningful deterioration will be censored at the time of the last available PRO assessment.

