
Key Secondary Objective 1:
 
To demonstrate the superiority of GSK3359609 in combination with pembrolizumab + 5FU-platinum chemotherapy compared to placebo in combination with pembrolizumab + 5FU-platinum chemotherapy in PFS in PD-L1 CPS \geq1 R/M HNSCC
 
(H4)
	Primary	PFS	
 • PD-L1 CPS \geq1 population (mITT) 	
 • New anti-cancer therapy: hypothetical • Treatment discontinuation: treatment policy • \geq2 missed disease assessments: hypothetical • Death: composite 	Hazard ratio for GSK3359609+pembrolizumab + 5FU-platinum chemotherapy vs. placebo+pembrolizumab + 5FU-platinum chemotherapy

Key Secondary Objective 2:
 
To demonstrate the superiority of GSK3359609 in combination with pembrolizumab + 5FU-platinum chemotherapy compared to placebo in combination with pembrolizumab + 5FU-platinum chemotherapy in TTD in pain in total population and PD-L1 CPS \geq1 R/M HNSCC
 
(H5, H6)
	Primary	TTD in pain	
 • Total population (mITT) • PD-L1 CPS \geq1 population (mITT) 	
 • New anti-cancer therapy: hypothetical • Treatment discontinuation: treatment policy • Disease progression per RECIST v1.1 or iRECIST: treatment policy • Death: treatment policy • \geq2 missed corresponding PRO assessments if at least 	Hazard ratio for GSK3359609+pembrolizumab + 5FU-platinum chemotherapy vs. placebo+pembrolizumab + 5FU-platinum chemotherapy

Objective (Hypothesis ¹)	Estimand Category	Estimand			
		Variable/ Endpoint ²	Population of interest (Analysis Set)	Intercurrent Event Strategy ³	Population Level Summary Measure
				one missed assessment is due to the participant being too ill: hypothetical	

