5.3. Appendix 3: Extended Time Without an Adequate Assessment

PFS

Given the scheduled disease assessment (i.e. starts at week 9 and then every 6 weeks; if study treatment discontinued after Week 51 then assessments will be every 12 weeks thereafter until the start of subsequent systemic anticancer therapy), the definition of 2 missed disease assessments will change. The following rules will be used for identifying the duration of extended time without an adequate assessment for PFS.

If the time difference between the event (PD/death) and last adequate disease assessment prior to the new anticancer therapy is more than the window, PFS will be censored at the last adequate disease assessment prior to the event (PD/death) and the new anticancer therapy.

- If the event is after Week 15 + 7 days and on or prior to week 51 + 7 days, then a subject will be identified as extended time without an adequate assessment if the subject did not have an adequate assessment during the time period of 98 days (12 weeks + 2-week windows) prior to the event;
- Else if the event is after Week 51 + 7 days and on or before Week 75 - 7 days then a subject will be identified as extended time without an adequate assessment if the subject did not have an adequate assessment during the time period of 140 days (18 weeks + 2-week windows).
- Else if the event is after Week 75 - 7 days then a subject will be identified as extended time without an adequate assessment if the subject did not have an adequate assessment during the time period of 182 days (24 weeks + 2-week windows).

TTD in Pain/PF

Given the scheduled PRO assessment for EORTC QLQ-H&N35 Pain domain and PROMIS-PF-8c (i.e. every 3 weeks till Week 21 and every 6 weeks afterwards), the definition of 2 missed disease assessments will change. The following rules will be used for identifying the duration of extended time without an adequate assessment for TTD in Pain or TTD in PF.

If the time difference between the event (deterioration) and last adequate corresponding PRO assessment prior to the new anticancer therapy is more than the window, TTD will be censored at the last available assessment prior to the event (deterioration) and the new anticancer therapy.

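### The TTD definitive-deterioration rule has no cut-off at new anticancer therapy, so a score taken after the switch can undo a deterioration seen before it

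*SAP*

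**What the plan says.** - **Event rule, SAP 4.3.1.1.** A meaningful deterioration must also be "Definitive, i.e. all subsequent assessment of the score are also showing a clinically meaningful deterioration compared with baseline". A second limb accepts the deterioration when nothing later was recorded, whatever the cause. Neither limb mentions new anticancer therapy.
- **Estimand, SAP 1.2.2, Table 2.** For TTD in pain and TTD in physical function the strategy is "New anti-cancer therapy: hypothetical".
- **Censoring, SAP 4.3.1.1, Table 4.** When new therapy starts before deterioration, the participant is "Censored at the date of last available corresponding PRO assessment on or prior to starting new anticancer treatment". Footnote 2, attached to the rows on missed assessments, adds: "The case where deterioration observed after the initiation of new anticancer treatment is described above and is not included in this situation". The SAP therefore foresees scores taken after new therapy.
- **Censoring, SAP 4.3.1.2.** Participants without a definitive deterioration are censored at their last visit, which is not the Table 4 date for someone who switched.
- **Protocol 9.4.3.** The confirmation rule is different: "two sequential assessments of the score are showing a clinically meaningful deterioration compared to baseline and no subsequent scores return to baseline". It has no cut-off at new therapy either. SAP 1.1, which lists changes from the protocol analysis, does not mention the difference.
- **PRO collection.** The protocol synopsis says that after treatment "participants will undergo follow-up assessments for safety, patient reported outcomes, PFS on first subsequent anti-cancer therapy (PFS2"), but it defers to the Schedule of Activities. Amendment 2 removed PROs and follow-up of subsequent therapy from that schedule.

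**The concern.** The hypothetical strategy asks about deterioration as if the new therapy had not been given, so a score obtained under that therapy should not decide whether an event occurred. Table 4 respects this when it sets censoring dates. The definitive check looks forward through every later score and does not.

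Best overall response shows the contrast. SAP 4.3.2 ends its window explicitly at progression or new anticancer therapy. PFS needs no such limit, because the first documented progression or death is the event and nothing later has to confirm it. TTD borrows PFS-style censoring rows and adds a look-ahead, and the gap arises there.

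Two things are at stake. Event status would depend on what next-line therapy did to symptoms. And a lost event becomes a censoring at a moment when the participant is deteriorated, so that censoring is informative. SAP 1.1 drops sensitivity and supplementary analyses from the abbreviated CSR, so no planned analysis would reveal the effect.

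**Working it through.** The documents give no event count, power or sample size for TTD, so there is no stated figure to reproduce. The check applies the rule to constructed records and then bounds the loss under open assumptions.

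**Step 1: apply the rule.** The visit schedule is from SAP 5.3 ("every 3 weeks till Week 21 and every 6 weeks afterwards"), giving Weeks 3, 6, 9, 12, 15, 18, 21 and 27. The participant is not deteriorated at Weeks 3 to 9 and is deteriorated at Week 12. New therapy starts at Week 16. Below threshold means that the change from baseline is less than a meaningful deterioration.

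| Record | SAP read literally | Look-ahead limited to scores on or before new therapy |
|---|---|---|
| (a) Deteriorated at 12 and 15; below threshold at 18, 21, 27 | Censored, Week 15 | Event, Week 12 |
| (b) Deteriorated at 12 and 15; below threshold at 18 only, deteriorated again at 21 and 27 | Censored, Week 15 | Event, Week 12 |
| (c) Deteriorated at 12, 15, 18, 21, 27 | Event, Week 12 | Event, Week 12 |
| (d) Deteriorated at 12 and 15; no later score | Event, Week 12 | Event, Week 12 |
| (e) Deteriorated at 12, recovered from 15 on | Censored, Week 15 | Censored, Week 15 |

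Records (a) and (d) are identical up to the switch and differ only in scores taken after it, yet one is a censoring and the other an event. Record (b) shows that a single below-threshold score is enough, even if the participant worsens again: the second deterioration starts after new therapy and so falls in the Table 4 censoring row. Record (e) shows that the limited rule still discards a deterioration that resolves before the switch.

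**Step 2: compare the protocol rule.** In record (a) the two deteriorated scores at Weeks 12 and 15 meet protocol 9.4.3 unless a later score returns to baseline. The SAP rule is undone by any later score below threshold. The gap is present in both documents and wider in the SAP.

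**Step 3: how many events could be lost.**

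Share of pre-switch events lost = P(new therapy after deterioration) × P(a post-switch score exists) × P(at least one post-switch score is below threshold)

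None of these is in the documents. Assumed ranges are 0.3 to 0.5, 0.25 to 1.0 and 0.2 to 0.6.

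- Lowest: 0.3 × 0.25 × 0.2 = 0.015, or 1.5%.
- Middle: 0.5 × 0.5 × 0.4 = 0.10, or 10%.
- Highest: 0.5 × 1.0 × 0.6 = 0.30, or 30%.

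The second factor matters most for this trial, because it depends on how many PRO scores were collected after new therapy and before PROs left the schedule.

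**The case against.** **The data may hardly exist.** The synopsis sentence on follow-up PROs defers to a schedule that no longer contains them, and SAP 1.3 lists only safety, PFS2 and survival for the same period. What is left is earlier records from participants who had stopped treatment, started new therapy and then completed a questionnaire. The documents do not show that there are any. This stands as a limit on size. It does not remove the defect in the rule, because footnote 2 to Table 4 provides for such scores.

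**A programmer could read Table 4 as governing the whole derivation** and drop post-switch scores throughout. That is a sensible reading, and placing record (a) in a row meant for therapy started before deterioration is awkward. But no line of the SAP tells the programmer to do this, and the stated rule says all subsequent scores.

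**Truncation makes its own assumption.** Whether the deterioration would have persisted without new therapy is unobserved, and a single bad score just before the switch would count as definitive. This is true, but the SAP already accepts it: a deterioration with no further score, for any reason, is definitive.

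**Formal testing is unlikely.** The PRO hypotheses H5 to H8 are tested only if OS is superior in both populations, in a study that has been terminated. This stands. TTD is still a secondary endpoint, and the main CSR will report its hazard ratios and confidence intervals.

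**Conclusion.** The point holds as a conflict between a stated rule and the estimand it serves. Followed literally, SAP 4.3.1.1 lets scores after new anticancer therapy cancel a deterioration observed before it, which the hypothetical strategy in Table 2 is meant to prevent. The TTD curves and hazard ratios for pain and physical function could be biased if switching, post-switch PRO completion or post-switch improvement differs by arm.

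A reader might infer more: that H5 to H8 are biased, and by a definite amount. For example, if one arm lost 5% of events and the other 14%, the ratio of retained proportions would be 0.95 / 0.86 = 1.10. The documents do not support this. They give no basis for any split between arms in this double-blind trial, the figure is not a Cox hazard-ratio bias, and the direction is unknown. The 1.5% to 30% range in the working rests wholly on assumed inputs and shows only how the loss would scale. The correction is worth making because the reported estimates depend on it and it is cheap.

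**What to change.** In SAP 4.3.1.1, state that PRO records dated after the start of new anticancer therapy are excluded before the definitive check and Table 4 are applied. A deterioration is then definitive if all later scores on or before that date are also deteriorated, or if no further such score exists.

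Two alignments should go with it:

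- Protocol 9.4.3 uses a different confirmation rule. Either bring it into line or record the departure in SAP 1.1.
- SAP 4.3.1.2 should point to the Table 4 censoring dates in place of the last visit.

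The cost is one sentence, one filter in the TTD derivation and two wording changes. The filter uses the start date of new therapy, which Table 4 already requires, so it asks for nothing beyond what the current rules need. The small downside is the one noted above: a lone deteriorated score just before a switch counts as definitive, as it already does when no later score is available.
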